7.4 Early Discontinuation of Subjects

It is the right and duty of the Investigator to discontinue a subject's participation if the subject's health or wellbeing is threatened by continuation in the study. In the event of premature discontinuation, the Investigator should determine the primary reason for discontinuation. A subject may be discontinued from the study if any of the following circumstances occur:

- The subject experiences a SAE rendering him or her unable to continue study participation.
- The subject experiences an AE that in the opinion of the Investigator may pose a significant risk for continued participation of the subject in the study.
- The subject is unable to physically or mentally tolerate the use of the investigational product.
- An exclusion criterion becomes apparent at any time during the study; the Medical Monitor must be contacted to discuss prior to discontinuing subject participation.
- The subject is not compliant with the study procedures; the Medical Monitor must be contacted to discuss prior to discontinuing subject participation.
- The subject voluntarily withdraws from the study. When possible, attempt to identify the reason the subject withdrew consent and document with particular attention paid to whether an underlying AE is at cause.
- The subject becomes pregnant.
- If for any reason per the Investigator's or the Sponsor's judgment, discontinuation is in the subject's best interest.

Subjects who discontinue the study prior to the completion of all treatment visits will be asked to complete the evaluations corresponding to Visit 12 (Day 43, End of Treatment). The Sponsor will be notified of early discontinuation as soon as possible during the study.

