8.1.7 Allergic Contact Dermatitis (Skin Sensitization) Assessment

Allergic contact dermatitis (ACD), as an AE, may manifest as moderate/severe pruritis and moderate/severe erythema with or without vesicles/bullae.

In the case of a suspected AE of ACD, the medical monitor should be contacted to discuss the case. If the medical monitor and the investigator agree that the AE is suggestive of ACD, the assigned treatment should be withheld, the AE documented, and treated, if required, by concomitant therapy that can include topical corticosteroids at the discretion of the investigator. Once the AE of ACD is resolved, in the opinion of the investigator, any concomitant therapy for this AE should be stopped, and the assigned treatment should be restarted (i.e., re-challenge exposure) after discussion with the medical monitor. If there is recurrence, an AE of ACD is confirmed and should be documented as an AE that is related to the assigned treatment.

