#### 1. PURPOSE OF THE ANALYSES

This statistical analysis plan (SAP) contains detailed information to aid in the implementation of the statistical analyses and reporting of the study data for use in the clinical study report (CSR) for study BBI-4000-CL-302. This SAP is being written with due consideration of the recommendations outlined in the most recent International Conference on Harmonisation (ICH) E9 Guideline, entitled Guidance for Industry: Statistical Principles for Clinical Trials, and the most recent ICH E3 Guideline, entitled Guidance for Industry: Structure and Content of Clinical Study Reports.

This SAP describes the data sets that will be used for analysis, as well as subject characteristics, efficacy, safety, and clinician-reported and patient-reported perception of disease severity and improvement parameters. The details of the specific statistical methods stated in the protocol will be provided and any changes from the protocol-specified analyses will be documented in the SAP prior to database lock. If additional analyses are required to supplement the planned analyses described in this SAP after the database lock, they may be completed and will be described in the CSR. Table, figure, and listing specifications are provided as an attachment in a separate document. This SAP amendment to version 1.1 dated July 06, 2021 is based on Amendment 3 of the BBI-4000-CL-302 protocol dated August 6, 2020 (Original September 27, 2019).

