#### 3. GENERAL ANALYSIS AND REPORTING CONVENTIONS

#### 3.1 Reporting Conventions

The following is a list of general analysis and reporting conventions to be applied to this study, unless otherwise specified.

All data displays (tables, listings, and figures) will have a header showing the sponsor company name, protocol number, page number, and display status (i.e. "DRAFT" or "FINAL"), as well as a footer indicating file name and run date/time. Summary tables and data listings will be summarized by treatment, as appropriate. All data collected perprotocol will be listed. Derived variables may also be listed.

Categorical variables will be summarized using counts (n) and percentages (%) and will be presented in the form "n (xx.x)." If a count is 0, no percentage will be shown. If a percentage is 100%, 100% will be shown with no decimal place. To ensure completeness, summaries for categorical variables will include all categories, even if no subjects had a response in a particular category. Unless otherwise specified, the denominator for each percentage will be based on the number of subjects with available data in the population being summarized. If there are missing values, counts will be shown but will not be included in percentage calculations.

Continuous variables will be summarized using mean, standard deviation (SD), minimum, maximum, median, and number of subjects. The mean and median will be reported to an additional level of precision than the original observation in its rawest form (i.e. on the eCRF), and the SD and other measures of variability (e.g. standard error) will be reported to two additional levels of precision than the original observations. The minimum and maximum will be the same precision as the original data. In general, any calculated values, such as those due to unit conversion, will be rounded to the same number of decimal places as the original data.

Unless otherwise specified, all statistical tests will be 2-sided using  $\alpha$ =0.05. Estimates and confidence intervals will be reported to 1 more decimal than the original data. P-values will be reported to 4 decimal places. P-values less than 0.0001 will be displayed as "<0.0001"; p-values greater than 0.9999 will be displayed as ">0.99999".

Summary tables and data listings:

- No preliminary rounding will be performed; rounding will only occur after analysis.

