# 9.2.1 Allergic Contact Dermatitis

Allergic contact dermatitis (ACD), as an AE, may manifest as moderate to severe pruritus and moderate to severe erythema with or without vesicles or bullae.

In the case of a suspected AE of ACD, the Medical Monitor should be contacted to discuss the case and the following steps should be taken at the discretion of the Investigator: 1) assigned treatment should be withheld, 2) the AE of ACD documented, 3) any necessary concomitant treatment should be administered, which can include topical corticosteroids.

Once the AE of ACD is resolved in the opinion of the Investigator, any concomitant therapy for this AE should be stopped, and the assigned treatment should be restarted after discussion with the Medical Monitor (i.e., re-challenge exposure). If there is a recurrence, ACD is confirmed and should be documented as an AE that is related to the assigned study treatment.

Confirmed ACD cases are defined as cases which led to recurrence of ACD event following treatment restart. Suspected ACD cases are those events with "Suspected Allergic Contact Dermatitis" checked on the AE eCRF page. The following parameters will be summarized with descriptive statistics by treatment group to characterize instances of ACD:

- Number and percentage of subjects with treatment-emergent ACD events by severity
- Number and percentage of subjects with treatment-emergent ACD events leading to treatment discontinuation by severity

- Number and percentage of subjects who restarted treatment after the ACD event and later discontinued treatment. These will be confirmed ACD events.
- Time to first confirmed ACD event in days defined as: start date of the ACD event treatment start date + 1.
- Time to first treatment interruption due to confirmed ACD event in days defined as: last exposure date prior to ACD event leading to interruption treatment start date + 1.
- Duration of treatment interruption in days defined as: date of first exposure after end of ACD event - date of last exposure prior to ACD event leading to interruption + 1. If the ACD event is ongoing, either the treatment discontinuation date or first available exposure date after the start of the event will be used to calculate duration. If subject experienced more than one interruption due to ACD, durations of interruptions will be summed.
- Time to treatment discontinuation in days defined as: date of treatment discontinuation date of treatment start + 1.

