- Time from treatment restart to treatment discontinuation due to recurrence ACD event in days defined as: date of treatment discontinuation date of first exposure after end of ACD event + 1.

Percentages will be out of the Safety Population in each group. A by-subject listing will also be presented.

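### SAP 9.2.1 defines confirmed allergic contact dermatitis by recurrence after restart, but the one count labelled confirmed is worded by restart and later discontinuation; the two should be reconciled

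*SAP*

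**What the plan says.** Protocol 8.1.7 describes withholding treatment for a suspected case and restarting it after resolution, and then gives the criterion: "If there is recurrence, an AE of ACD is confirmed and should be documented as an AE that is related to the assigned treatment". SAP 9.2.1 repeats that rule and adds a definition for analysis: "Confirmed ACD cases are defined as cases which led to recurrence of ACD event following treatment restart". Neither statement mentions discontinuation.

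The SAP section then lists the parameters to be summarised. Three are numbers and percentages of subjects. The first covers all treatment-emergent ACD by severity and the second covers ACD that led to treatment discontinuation by severity; neither is labelled confirmed. The third reads: "Number and percentage of subjects who restarted treatment after the ACD event and later discontinued treatment. These will be confirmed ACD events".

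The word confirmed also appears in two time variables: time to first confirmed ACD event, and time to first interruption due to a confirmed ACD event. The last item in the list does name recurrence, but it is a duration: "Time from treatment restart to treatment discontinuation due to recurrence ACD event in days defined as". Percentages use the Safety Population in each group as denominator.

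**The concern.** The definition and the count sit in the same section and are worded by different criteria. Re-challenge is what separates a suspected case from a confirmed one, and a confirmed case is to be recorded as related to the assigned treatment. The confirmed percentage in each arm should therefore follow the re-challenge result. As the text stands, two programmers could each follow SAP 9.2.1 faithfully and produce different confirmed counts. The two time variables inherit the same uncertainty about which subjects enter them.

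**Working it through.** The plan states no figure for ACD, so there is nothing to reproduce. The check sets the definition beside the count item for a subject who has an ACD event and restarts treatment.

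| After restart | Definition sentence | Count item, read literally | Count item, read as subset of confirmed |
|---|---|---|---|
| Recurrence, treatment later stopped | confirmed | counted | counted |
| Recurrence, treatment not stopped | confirmed | not counted | not counted |
| No recurrence, treatment later stopped | not confirmed | counted | not counted |
| No recurrence, treatment not stopped | not confirmed | not counted | not counted |

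**Literal reading.** The item and the definition disagree in the second and third rows, in opposite directions. The count can be too low, too high, or right by cancellation.

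**Subset reading.** The third row drops out and nobody is mislabelled. The second row remains uncounted, so the item is not the number of confirmed cases. The other two count items do not supply that number, because neither is limited to confirmed cases.

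**Can the disputed rows occur?**

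- Second row: neither document says that every recurrence ends treatment. The rule for duration of interruption allows for repeats: "If subject experienced more than one interruption due to ACD, durations of interruptions will be summed". A subject can therefore resume after one ACD interruption and be interrupted again. This shows that the pattern is foreseen, not how often it would happen.
- Third row: a subject who leaves the study early also stops treatment, and protocol 7.4 lists reasons unrelated to ACD, such as voluntary withdrawal. The opening of that section, "A subject may be discontinued from the study if any of the following circumstances occur", concerns leaving the study, so it does not show what follows a recurrence.

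**Size.** No ACD, restart or recurrence rate is given, so the number of affected subjects cannot be derived. As a unit conversion only, if the Safety Population is close to the 175 per arm planned in protocol section 2, one subject is 100/175 = 0.57 percentage points of an arm.

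**The case against.** The best reply is that the item is shorthand. The definition stands just above the list, so calling these subjects confirmed can be taken to import the recurrence condition. The last item, which ties restart-to-discontinuation to recurrence, suggests the authors meant exactly that. This stands, and it means a reader should not infer that the row is certainly wrong. What the documents support is that the wording is wrong if followed literally and incomplete if followed charitably.

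A second reply is that a definition-based count is available anyway. SAP 3.1 says: "Continuous variables will be summarized using mean, standard deviation (SD), minimum, maximum, median, and number of subjects". If the definition governs time to first confirmed ACD event, the number of subjects shown for that variable is the number of confirmed cases, and dividing by the Safety Population gives the percentage. This also largely stands, so it would go too far to say the plan yields no count on its own definition. It depends on the definition governing that variable, which the SAP does not say outright, and a headline safety percentage should not have to be recovered from the n of another row.

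Third, the table itself may resolve the matter: "Table, figure, and listing specifications are provided as an attachment in a separate document". The rows of Table 14.3.1.9 cannot be seen, so the supportable claim is that the SAP 9.2.1 list names no such row, not that the table lacks one.

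Finally, one might infer that ACD cases could be lost. They would not be. All treatment-emergent ACD is counted by severity, ACD leading to treatment discontinuation is counted separately, the general tables in SAP 9.2 cover treatment-related events and events leading to dose interruption, and a by-subject ACD listing is planned. Only the confirmed label is at stake.

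**Conclusion.** The inconsistency is real and minor. By the plan's own definition, recurrence after restart is sufficient for confirmation. The single number-and-percentage item carrying that label describes restart plus later discontinuation. Either the item departs from the definition, or it is a correct subset and the list names no number and percentage for all confirmed cases. The definition is the better anchor: it agrees with the protocol, the SAP revision history records that it was deliberately refined in version 1.1, and SAP section 13 records no change of ACD criterion from the protocol.

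The size cannot be estimated from the documents and may be zero. The consequence is limited to the descriptive ACD summary. The conclusion assumes only that the separate table specification does not already settle the point.

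**What to change.** Derive one confirmed-ACD flag from the existing definition sentence: recurrence of ACD after treatment restart, whether or not treatment was later discontinued. Use it for the number and percentage of confirmed cases and to select the subjects for both time variables that say confirmed. For those variables, also state whether the start date of the ACD event means the first event or the recurrence; the flag alone does not settle that. If restart followed by discontinuation is still of interest, keep it as a separate row without the confirmed label.

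The cost is a few lines of SAP text and a small amount of programming. The inputs are already collected: AE start and resolution dates and action taken with study drug (protocol 9.2.1.2), the suspected-ACD box on the AE form (SAP 9.2.1), and dose interruptions on the dosing page (SAP section 7). The flag relies on recurrences being recorded as AEs, which protocol 8.1.7 already requires. Whether a table shell must change cannot be told from the documents. The change concerns reporting only and alters no clinical procedure.

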# 9.3 Local Tolerability Assessments

Local tolerability assessments are performed for both axillae individually at visits 4, 5, 6, 7, 8, 9, 12 (EOT), and 13 (follow-up). Visit 4 data are the baseline. Should Visit 4 data be missing, baseline will be derived as the last value prior to first dose and as such unscheduled visits may be included. Subjects rate the severity of any symptoms of burning, stinging, or itching at the application-site on a scale of 0 = absent, 1 = minimal, 2 = mild, 3 = moderate, and 4 = severe. Investigators assess the drug application site for the existence of significant local symptoms of scaling and erythema on a scale of 0 = absent, 1 = minimal, 2 = mild, 3 = moderate, and 4 = severe. For any symptoms, subject severity is the worst severity of the two axillae.

Subject and Investigator assessments will be included in tables and listings. Tables will be presented by treatment arm. An overall summary table will be presented with subject incidences tabulated according to the worst severity experienced while on study. At each visit, local tolerability assessments will also be descriptively summarized by severity. Additionally, at each post-baseline visit, local tolerability will be summarized as cumulative shift tables vs. baseline. Subject counts for each symptom will be cross-tabulated with baseline severity according to the maximum post-baseline severity reported for either axilla up to the current visit. Local tolerability assessment results will also be plotted by severity, displaying counts for any symptom, burning, stinging, itching, scaling, and erythema. A symptom is counted if the severity scale is rated >0.

## 9.4 Clinical Laboratory Evaluation

Safety laboratory parameters (hematology, chemistry, urinalysis) will be collected at the Screening Visit and EOT Visit. Urine pregnancy results will be collected at visits 1, 4, 8, and 12 (EOT). Laboratory parameters will be presented in Systeme International (SI) units and descriptively summarized for values at each visit and for changes from baseline at each subsequent visit. Unscheduled visits and early termination visits will be included.

Laboratory parameters to be summarized and listed include hematology, clinical chemistry, and routine urinalysis. Urine pregnancy test results will be listed only.

# 9.5 Vital Signs, Physical Findings, and Other Observations Related to Safety

## 9.5.1 Vital Signs

Vital signs measurements will be collected at Visits 4, 5, 6, 7, 8, 9, 12 (EOT), and 13 (follow-up). Visit 4 data are the Baseline. Should Visit 4 data be missing, baseline will be derived as the last value prior to first dose (e.g. Screening), and, as such, unscheduled visits may be included. Vital sign measurements will include systolic and diastolic blood pressure, pulse rate, respiratory rate, and temperature. Vital sign parameters will be descriptively summarized for values at each visit and for changes from baseline at each subsequent visit. Vital signs will also be listed.

# 9.5.2 Physical Examinations

Physical examination results will be collected at Visit 4 only. Physical examination will include assessments of the head, eyes, ears, nose, throat, skin, thyroid, neurological, lungs, cardiovascular, abdomen (liver and spleen), lymph nodes, and extremities. Height and weight will also be measured and recorded. Results of the physical examination will be presented in subject data listings by subject, study visit, and body system.

# 9.5.3 Other Safety Measures

#### 9.5.3.1 Prior and Concomitant Medications

Medications will be coded using the latest version of the World Health Organization (WHO) drug dictionary. Medications entered on the eCRF will be mapped to Anatomic Therapeutic Chemical (ATC) drug class (level 4) and drug name.

Prior and concomitant medications will be summarized separately and the study phase of each medication will be determined programmatically based on medication start and end dates. Partial or missing start and end dates will be imputed according to Section 9.2.

A prior medication is defined as any medication started prior to the date of the first dose of study drug. A concomitant medication is defined as any medication started on or after the date of the first dose of study drug. For the summary of both prior medications and concomitant medications, the number and percentage of subjects receiving any medication will be summarized by treatment group, as will the number and percentage receiving any medication by ATC drug class and generic drug name. Subjects reporting use of more than one medication at each level of summarization (any medication received, ATC class, and generic drug name) will be counted only once. ATC class terms will be displayed by descending order of incidence, as will generic drug names within each ATC class. The study phase during which each medication was received (e.g., prior, concomitant,) will be presented on the listing of prior and concomitant medications.

Prior or concomitant therapies and procedures will be listed only.

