4.3 Exclusion Criteria

Meeting any of the following criteria will exclude a subject from participating in this study:

- 1. In the Investigator's opinion, diagnosis of any skin or subcutaneous tissue conditions of the axilla(e), (i.e., the axillary area should be deemed otherwise "normal", besides the hyperhidrosis diagnosis, and free of blisters, boils or sinus tracts, significant scarring, or open wounds).
- 2. Prior use of any prohibited medication(s) or procedure(s) for the treatment of axillary hyperhidrosis within the specified timeframe:
 - a. Botulinum toxin to the axillary area within 9 months of GSP1 (Visit 2).
 - b. Prior treatment with axillary iontophoresis within 4 weeks of GSP1 (Visit 2)
 - c. Axillary thermolysis, sympathectomy, or any other treatment with a medical device or surgical procedure of the axillary area at any time in the past. Prior axillary laser hair removal is permitted if more than 28 days prior to GSP1 (Visit 2).
 - d. Serotonergic agonist (or drugs that increase serotonin activity including selective serotonin re-uptake inhibitors [SSRIs]), beta-blocker, alpha-adrenergic agonist (clonidine), dopamine partial agonist, or tricyclic antidepressant treatment within 28 days of GSP1 (Visit 2). However, a subject who has been on a stable dose (in the opinion of the Principal Investigator) of any of these medications and has not had a recent change in hyperhidrosis frequency or severity for 3 months prior to the baseline visit may be included. Doses of these agents should not be altered during the course of the study.
 - e. Any topical treatment for hyperhidrosis, requiring a prescription, within 28 days of GSP1 (Visit 2).
 - f. Any over-the-counter topical antiperspirant/deodorant (applied directly to the axilla[e]) within 7 days of GSP1 (Visit 2). Non-antiperspirant deodorant will be provided by the Sponsor.
- 3. Anticholinergic agents used to treat conditions such as, but not limited to, hyperhidrosis, asthma, incontinence, gastrointestinal cramps, and muscular spasms by any route of administration (e.g., intravenous [IV], oral, inhaled, topical, etc.) within 28 days of GSP1 (Visit 2).
- 4. All oral or topical homeopathic or herbal treatment (i.e., alternative therapies such as sage tablets, chamomile, valerian root, and St. John's wort) within 28 days of GSP1 (Visit 2).

- 5. Use of any cholinergic drug (e.g., bethanechol) within 28 days of GSP1 (Visit 2).

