6 CONCOMITANT MEDICATIONS/TREATMENTS

Information will be recorded on concomitant medications/treatments (e.g., aspirin, Tylenol, birth control pills, intrauterine device [IUD], vitamins) taken during study participation, or which may require a washout for study participation. Every effort should be made to keep dosing with any concomitant medications consistent/constant during the study.

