| 14.3.1.8.9  | Number and Percentage of Subjects with
Anticholinergic Treatment-Emergent Adverse Events
Cumulative to Visit 13 (Day 57, Follow-up) by System
Organ Class, Preferred Term, and Maximum Severity     | Safety     |
| 14.3.1.8.10 | Number and Percentage of Subjects with Local Site
Reaction Treatment-Emergent Adverse Events
Cumulative to Visit 14 (Day 57, Follow-up) by System
Organ Class, Preferred Term, and Maximum Severity | Safety     |
| 14.3.1.9    | Summary of Subjects with Allergic Contact Dermatitis   | Safety     |
| 14.3.4.1    | Mean and Mean Change from Baseline in Serum
Biochemistry Values by Visit  | Safety     |
| 14.3.4.2    | Mean and Mean Change from Baseline in Hematology
Values by Visit  | Safety     |
| 14.3.4.3    | Mean and Mean Change from Baseline in Continuous
Urinalysis Values by Visit   | Safety     |
| 14.3.4.4    | Categorical Urinalysis Values by Visit   | Safety     |
| 14.3.5      | Study Drug Administration Exposure and Compliance  | Safety     |
| 14.3.6.1    | Worst Post-baseline Severity for Local Tolerability
Assessments by Treatment Group  | Safety     |
| 14.3.6.2    | Worst Severity for Local Tolerability Assessments by
Treatment Group and Visit  | Safety     |
| 14.3.6.3    | Shift in Worst Severity for Local Tolerability
Assessments from Baseline to Each Visit  | Safety     |
| 14.3.6.4    | Mean and Mean Change from Baseline in Vital Signs
Values by Visit   | Safety     |
| 14.3.6.5    | Summary of Concomitant Medications by Drug Class
and Generic Drug Name  | Safety     |

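### SAP 9.5.3.1 classifies medications by start date alone, so a drug with a known start before first dose that continues on treatment is summarized as prior only and is missing from the concomitant table

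*SAP*

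**What the plan says.** SAP 9.5.3.1 gives two definitions, each resting on the start date:

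- Prior: begun before first dose, with no condition on when the drug stopped.
- Concomitant: "A concomitant medication is defined as any medication started on or after the date of the first dose of study drug"

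The same section says that "Prior and concomitant medications will be summarized separately" and that "the study phase of each medication will be determined programmatically based on medication start and end dates". Partial or missing start and end dates are to be imputed by the rules in SAP 9.2. The combined listing is to show the phase in which each medication was received.

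The planned outputs are Table 14.1.5 (prior) and Table 14.3.6.5 ("Summary of Concomitant Medications by Drug Class" and generic name), both in the Safety Population and both by treatment group, plus Listing 16.2.4.3, which covers both kinds.

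Protocol section 6 uses the term more widely: "Information will be recorded on concomitant medications/treatments (e.g., aspirin, Tylenol, birth control pills, intrauterine device [IUD], vitamins) taken during study participation". Protocol 4.3 admits subjects on stable serotonergic drugs, beta-blockers, clonidine, dopamine partial agonists, tricyclics, anti-anxiety or antidepressant drugs and psychostimulants. It also allows drugs with anticholinergic side effects at the investigator's discretion. Of these agents it says: "Doses of these agents should not be altered during the course of the study".

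**The concern.** A concomitant-medication table is normally read as showing what subjects were taking while on study drug. Here the definition answers a different question: what they began after dosing started.

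The gap falls on drugs of interest in this trial. The permitted background classes can affect sweating or add anticholinergic effects, and the SAP tabulates anticholinergic TEAEs separately. Protocol 6.2 prohibits adding these classes, or changing their dose, during the study. In a compliant subject, use of these classes is therefore continuing background use, which the rule keeps out of the concomitant table. With known start dates, they would reach that table mainly when newly added contrary to 6.2.

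At stake is whether a reader of the study report can see on-treatment background use by arm.

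**Working it through.** No arithmetic applies. The plan gives no figure on this point, so the check is to apply the two definitions to each possible date pattern. D1 is the date of first dose.

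| Pattern | Taken on treatment? | Class under SAP 9.5.3.1 | Class if continuing drugs also count as concomitant |
|---|---|---|---|
| (a) start before D1, end before D1 | No | Prior only | Prior only |
| (b) start before D1, end on or after D1, or ongoing | Yes | Prior only | Prior and concomitant |
| (c) start on or after D1 | Yes | Concomitant only | Concomitant only |

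**Step 1: the two definitions.** They are mutually exclusive and together cover every known start date. No rule places a drug in both groups. Pattern (b) is the only one whose label disagrees with when the drug was taken.

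**Step 2: consistency within SAP 9.5.3.1.** The section says phase is "determined programmatically based on medication start and end dates" and provides for imputing end dates, yet no end date enters either definition. It also says the listing shows the phase in which a drug was received. For pattern (b) the label would show only when it was started.

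**Step 3: consistency with the protocol.** Protocol section 6 ties the term to use during participation, whatever the start date. SAP section 13, which records changes from the protocol, does not mention a narrower meaning.

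**Step 4: where pattern (b) drugs go.** They go to Table 14.1.5, by arm, ATC class and generic name, and to Listing 16.2.4.3. Table 14.1.5 also holds pattern (a) drugs. These are expected too: Protocol section 6 records drugs that may need a washout, and Protocol 7.2.2 requires washouts to be finished before Visit 2. A washed-out drug and one used on all 42 treatment days are counted alike.

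**Step 5: exceptions through start-date imputation.** SAP 9.2 sets a start date to treatment start in three cases: the date is completely missing; only month and year are known and both match treatment start; or only the year is known and it matches. An ongoing drug with such a date is classed as concomitant. The pattern (b) result is therefore exact for known start dates only.

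**Step 6: what happens once end dates are used.** SAP 9.2 imputes end dates in the same way, substituting end of treatment or end of study without saying which applies. Two errors become possible:

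- A drug stopped before D1, with only the year of stopping known and that year matching, would be moved to end of treatment or study and become concomitant.
- A drug stopped after D1 on an unknown day of a month before the end-of-treatment or end-of-study month would be set to the 1st of that month. If it stopped in the month of D1, the imputed date falls on or before D1. This can arise in any completer, because 42 days exceeds the 31 days of the longest month, so D1 and end of treatment lie in different months.

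**The case against.** The strongest reply is that little is lost. Every drug with a known start before dosing is still tabulated by arm, in the same Safety Population, in Table 14.1.5, and is listed in 16.2.4.3. Where the protocol requires stable dosing before entry and no change on study, background use resembles a baseline characteristic, and a prior table by arm is a reasonable place for it. The concomitant table would show the newly started drugs, which are the post-randomization changes that Protocol 6.2 is concerned with. On-study use of a prohibited drug is a major violation category under SAP 5.2. The reference to end dates may also mean that the definitions are a drafting slip that programming would put right.

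Most of this stands, and it rules out three stronger readings that a reader might infer:

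- **That no ongoing drug can ever appear as concomitant.** The start-date imputation in SAP 9.2 moves some into that group.
- **That an imbalance between arms in background drugs would be invisible.** An imbalance in, say, SSRIs could be seen in Table 14.1.5. What cannot be seen there is how much of that use continued on treatment.
- **That the GSP or HDSM-Ax-7 results are put at risk.** The rule enters no efficacy model, imputation of efficacy data, error rate or TEAE definition. The per-protocol criterion on interfering medications does not refer to SAP 9.5.3.1.

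The reply does not remove the contradiction within the section. Hoping that programming departs from two explicit definitions is not a specification, and Table 14.1.5 cannot separate stopped drugs from continued ones.

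**Conclusion.** The point holds in a limited form. Followed as written, SAP 9.5.3.1 omits from Table 14.3.6.5 every drug with a known start before first dose that continued on treatment, and gives it the wrong phase in Listing 16.2.4.3. What is lost is any planned table showing on-treatment background use by arm. The consequence is descriptive only.

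The number of subjects or drugs affected cannot be stated, because the documents give no medication data. The conclusion assumes that the definitions are programmed literally and that start dates are known or are not imputed to treatment start. It is worth correcting because the table would not show what its title says and the correction is small.

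**What to change.** Revise SAP 9.5.3.1 as follows:

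1. Define concomitant as any medication taken at any time from the first-dose date onward: begun on that date or later, or begun before it and either ongoing or stopped on that date or later.
2. Keep prior as begun before first dose. Continuing drugs are then flagged in both phases, in the tables and in the listing. Use this one scheme throughout.
3. State that end-date imputation under SAP 9.2 must not override known information on whether the drug had stopped before first dose or was ongoing. Say which of end of treatment and end of study is used for medications.

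The cost is a few sentences in the SAP, a change to the derivation of the phase flag, and footnotes to Tables 14.1.5 and 14.3.6.5. No new data are needed if the end date and ongoing status are already recorded. The section's own use of end dates suggests the end date is, but the case report form is not in the documents and should be checked. If the database is already locked, the revised summary can be added and described in the study report, as SAP section 1 allows.
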